## **8 Protocol Deviations and Analysis Sets**

### **8.1 Definition of Protocol Deviations and Analysis Sets**

Important protocol deviations are protocol deviations that might significantly affect the completeness, accuracy, and/or reliability of the study data or that might significantly affect a subject's rights, safety, or well-being. Important protocol deviations are defined in the latest version of document named MS200527-0060\_List\_of\_IPDs\_Version 2.0\_24JUL2019.docx.

All deviations will be identified and confirmed prior to or at the Data Review Meeting (DRM), which will occur before the database lock, including clinically important deviations if leading to the exclusion of a subject from PP analysis set (see Section 8.2).

The outcome of the DRM will document the important protocol deviations as well as the finalization of the analysis populations in a memo. Important protocol deviations will be documented in Clinical Data Interchange Standards Consortium Study Data Tabulation Model (SDTM) whether identified through sites monitoring, medical review and/or programming.

### **8.2 Definition of Analysis Sets and Subgroups**

#### **8.2.1 Sample Size**

The primary endpoint of the trial is the ACR20 response at Week 12. A sample size of 80 evaluable subjects per group will provide approximately 90% power at an  $\alpha$  of 0.05, 2-sided significance level to detect a difference in Week 12 ACR20 response proportion between evobrutinib- and placebo-treated subjects, assuming a placebo response proportion of 30% to 45% and an expected treatment benefit of 30%, after adjusting for multiple comparisons of 3 dose comparisons with placebo. For the same range of placebo response rate, the sample size of 80 evaluable subjects per group will also provide adequate power (approximately 80%) for the expected difference of 25%. To account for reduced information provided by the Modified Intent-to-Treat (mITT) analysis set, due to subject dropout and protocol noncompliance, occurring at a rate of approximately 11% over a 12-week period, approximately 90 subjects per group will be enrolled.

[figure not shown]
#### **8.2.2 Analysis Sets**

Table 2 provides the definitions of the Analysis Sets and their purposes.

**Table 2: Analysis Sets**

Analysis Set	Definition	Purpose
Screening Analysis Set (SCR)	The SCR includes all subjects who signed the informed consent.	The purpose of this analysis set is to count how many subjects signed the informed consent
Intent-To-Treat (ITT) Analysis Set	The ITT analysis set will include all subjects randomly allocated to a treatment, based on the intention to treat “as randomized” principle (i.e., the planned treatment regimen rather than the actual treatment given in case of any difference).	The ITT Analysis Set will be used for TLFs based on randomized subjects, such as randomization listing and TLFs on protocol deviations.
mITT Analysis Set	The mITT analysis set will include all randomized subjects who received at least one dose of IMP (evobrutinib or placebo). Subjects in the mITT analysis set will be included in the treatment group as randomized.	The mITT Analysis Set will be used for demographic/baseline characteristics and efficacy endpoints.
Quality of Life (QoL) Analysis Set	The QoL Analysis Set will include all randomized subjects who have received at least one dose of IMP (evobrutinib or placebo) and have at least one Baseline and one post-Baseline QoL assessment (among the following: HAQ-DI, SF-36, FACIT, CCI [REDACTED]). Subjects will be analyzed according to randomized treatment.	The QoL Analysis Set will be used for QoL endpoints.
Safety Analysis Set (SAF)	The SAF analysis set will include all subjects who receive at least 1 dose of IMP (evobrutinib or placebo). Subjects will be analyzed according to the actual treatment they receive. The SAF will be used for safety analyses.	The SAF will be used for medications, exposure/compliance and safety endpoints.
PP Analysis Set	The PP analysis set will include all mITT subjects who do not have any clinically important protocol deviations before or at the time of Week 12 visit. Subjects in the PP analysis set will be included in the treatment group as randomized. Clinically important protocol deviations related to MRI assessments (protocol deviation PDEV63 from the List of Important Protocol Deviations) will not be considered.	The PP analysis set will be used for the primary and key secondary efficacy endpoints.
MRI Analysis Set	The MRI analysis set will include the mITT subjects who have at least 1 pre-dose and 1 post-dose MRI assessment. Subjects in the MRI analysis set will be included in the treatment group as randomized.	The MRI Analysis Set will be used for all the analyses of the MRI endpoints.

MRI PP Analysis Set	The MRI PP analysis set will include all MRI subjects who do not have any clinically important protocol deviations before or at the time of Week 12 visit. Subjects in the MRI PP analysis set will be included in the treatment group as randomized. All clinically important protocol deviations (including protocol deviation PDEV63 from the List of Important Protocol Deviations) will be considered.	The MRI PP analysis set will be used for the MRI endpoints.
---------------------	---	---

### 8.2.3 Subgroup Analysis

Table 3 below defines the subgroups to be used for subgroup analysis as described in Section 14 and Section 15.

**Table 3: Subgroups**

Subgroup	Content	Definition
A	MRI sub-study participation	Yes; No (from IWRS – Is the subject participating in the MRI substudy?)
B	Gender	Male; Female (from DEMO form of electronic case report form [eCRF])
C	Region	US; Western Europe; ROW (from IWRS)

## 9 General Specifications for Data Analyses

All statistical analyses will be performed by PPD, except the modeling and simulation analysis, which will be performed by Merck KGaA / EMD Serono Research & Development Institute, Inc.

### 9.1 Actual Treatment Assignment

A subject who received 2 different types of treatment regimen over the course of treatment should be tabulated according to the treatment regimen received most frequently. If there is a “tie”, the highest dose will be chosen.

### 9.2 Presentation of Tables/Listings/Figures (TLFs)

Tables and figures will be sorted by treatment group (in the order stated in Table 4) and chronological time point (where applicable).

**Table 4: Treatment Groups and Regimens**

Treatment Group	Regimen	Presentation for the 12-week treatment period	Presentation for the OLE (*)
1	Placebo	Placebo	Placebo/Evobrutinib 50 mg BID
2	Evobrutinib 25 mg QD (once daily)	Evobrutinib 25 mg QD	Evobrutinib 25 mg QD/Evobrutinib 50 mg BID
3	Evobrutinib 75 mg QD	Evobrutinib 75 mg QD	Evobrutinib 75 mg QD/Evobrutinib 50 mg BID
4	Evobrutinib 50 mg BID (twice daily)	Evobrutinib 50 mg BID	Evobrutinib 50 mg BID/Evobrutinib 50 mg BID

(\*): As detailed in Section 7, some subjects have entered in the OLE, even if the Sponsor decided not to initiate the OLE in CTP V3.0. Subjects who agreed to participate in the OLE were administered evobrutinib 50 mg BID.

All data recorded during the trial will be presented in individual data listings (in the order stated in Table 4). All listings are sorted by treatment group, subject, and time point (where applicable), if not otherwise stated.

### 9.3 Data handling for the planned analyses

As the database lock will be based on data up to and including the last patient’s last visit, all data from screening up to and including the Safety Follow-up visit for all subjects will be locked and available in the database for the final analysis.

## 9.4 Presentation of continuous and qualitative variables

Continuous variables will be summarized using descriptive statistics, ie,

- number of subjects (N)
- number and percentage of non-missing values
- number and percentage of missing values
- mean, standard deviation (SD)
- median, 25th Percentile - 75th Percentile (Q1-Q3)
- minimum and maximum

Unless otherwise specified, the number of digits for non-derived and derived data, presented in outputs or available in ADaM datasets, is specified in the Biostatistics Outputs Assembly (BOA) document. For efficacy endpoints from Section 14, median and SD will be presented with 1 more digit compared to the original data, whereas mean, min, max, Q1-Q3 will be presented with the same number of digits as the original data.

For both continuous and qualitative variables, percentages such as 0% or 100% should be reported with the same format used for the column, together with the count of observations. For example, if the count of observations is zero, then display ‘0 (0.0)’; if the count of observations represents 100%, then display ‘xx (100.0)’.

Qualitative variables will be summarized by counts and percentages. Unless otherwise stated, the calculation of proportions will be based on the number of subjects in the analysis set of interest. Therefore, counts of missing observations will be included in the denominator and presented as a separate category.

In case the analysis refers only to certain visits, percentages will be based on the number of subjects in the analysis set of interest, unless otherwise specified. Total of missing and non-missing observations at each time-point will reflect the population still in the trial at that time. For example, if a subject is still in the trial at the time-point but with missing data, it should be counted in the number of missing observations.

CCI [REDACTED]

CCI [REDACTED]

[REDACTED]

[REDACTED]

Mean, Min, Median, Max: 3 significant digits  
SD: 4 significant digits  
CV%: 1 decimal place

## 9.5 Definition of baseline

For the purpose of statistical analysis, baseline is defined as the last non-missing measurement prior to the first dose of study drug as described in [Table 5](#):

**Table 5: Definition of Baseline**

Randomized	Time Period	Baseline

 
• Placebo
 
• Evobrutinib 25 mg QD
 
	12-week treatment period	Last non-missing measurement prior to first dose of study drug of the 12-week treatment period

 
• Evobrutinib 75 mg QD
 
• Evobrutinib 50 mg BID
 
	OLE Period	Last non-missing measurement prior to the first dose of evobrutinib of the OLE period

## 9.6 Other Specifications

### Difference between the randomization strata (MRI site) and MRI substudy participation

In case of difference between the two variables “Was the subject enrolled in an MRI site?” and “Did the subject participate in the MRI substudy?”, the MRI substudy participation will be used for the statistical analysis.

### Definition of Change from Baseline (CFB):

CFB and percent CFB will be computed as follows:

- $CFB = \text{visit value} - \text{baseline value}$
- $\text{Percent CFB} = 100 * (\text{visit value} - \text{baseline value}) / \text{baseline value}$

### Definition of duration:

Unless otherwise specified, duration will be calculated as the difference between start and stop date + 1 (e.g. duration of AE (days) = AE stop date – AE start date + 1). Unless otherwise specified, missing dates will not be imputed.

### Conversion factors:

The following conversion factors will be used to convert days into months or years: 1 month = 30.4375 days, 1 year = 365.25 days. For time windows calculation, 1 month is expressed as 30 days.

### Definition of Body Mass Index (BMI) (kg/m^2):

BMI will be computed as  $\text{weight} / (\text{height}^2)$ , where weight is expressed in kg and height in m.

### Handling of missing data:

For efficacy analysis, methods of missing data handling are detailed in Section 14.

Unless otherwise specified, missing data will not be replaced.

In all subject data listings, imputed values will be presented. In all listings imputed information will be flagged. Non-imputed partial dates will be presented in a format such as “\_\_\_\_YYYY”. Where imputation is defined, an imputed date with flag (ie, D for day, M for month) will be reported.

Missing statistics, eg when they cannot be calculated, should be presented as ‘NE’ (denoting “Not Evaluable”). For example, if n=1, the measure of variability (SD) cannot be computed and should be presented as ‘NE’.

In case of zero records, an empty output with 0 occurrences, or a sentence mentioning that there are no data, will be presented. For tables of AEs and Deaths (outputs required for EudraCT and/or clinicaltrials.gov), if there are no observations, the output must contain the first line ‘Subjects with...’ or ‘Subjects who died’ displayed with 0 occurrence.

If the System Organ Class (SOC) or Anatomical Therapeutic Class (ATC) term is missing/not coded yet, then ‘Uncoded SOC’ (or ‘Uncoded ATC’) will be indicated at the TLF level. When a Preferred Term (PT) is missing, it will be set to ‘Uncoded PT: verbatim text’.

### Treatment day:

Treatment day is defined as relative day to the start date of treatment. Treatment day will be calculated accordingly, ie:

- For the 12 weeks treatment period, treatment day 1 is defined as the date of first administration of any IMP.
- For the OLE period, treatment day 1 is defined as the date of first administration of evobrutinib 50 mg BID during OLE.

The day before is defined as Treatment day –1 (no Treatment day 0 is defined).

Treatment day will only be presented in subject safety data listings. In these listings, the difference (in days) between an event (eg, AE or laboratory assessment) and the first administration will be calculated as follows:

- If the event is posterior to the first IMP administration, the difference is equal to Date of event – Date of first IMP administration + 1
- Otherwise, the difference is equal to Date of first IMP administration – Date of event

### Time windows

As a measurement may have been performed out of window, data will be re-allocated according to time windows, so that each measurement is allocated to the closest time point.

Appendix 18.6 provide further details of time window allocations for safety and efficacy endpoints.

For efficacy and safety analyses, each measurement will be assigned an analysis visit number first. The analysis visit will then be used for all missing data imputations, analysis variable derivations, statistical calculations and presentations.

For patient data listings by time point, the nominal visit (as collected in the database) as well as the analysis visit will be displayed.

For time windows calculation, 1 month is expressed as 30 days.

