### 7.1.2 Treatment Period

At all applicable visits, patient-reported outcome questionnaires must be performed prior to any other assessments. At the Day 1 visit, assessments should be performed prior to randomization and the administration of the IMP. Scheduled assessments will be performed according to [Table 1](#) before administration of the IMP, with the exception of relevant postdose blood draws (eg, [CCI](#)). The first dose of the IMP will be given while the subject is still on site for the Day 1 visit.

At subsequent visits (Weeks 2 through 12), all scheduled visits during the Treatment Period may take place within the visit windows specified in [Table 1](#). Subjects who discontinue early must return for the End of Treatment/Early Withdrawal Visit and Safety Follow-up Visit.

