#### 7.1.2.1 End of Treatment Visit

The End of Treatment Visit will be performed at Week 12 or within 5 days of early discontinuation of treatment with the IMP. Subjects will undergo assessments as described in [Table 1](#). In case of premature discontinuation, the PRO assessments have to be completed at the End of Treatment visit.

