#### **7.1.4 Safety Follow-up Visit**

The Safety Follow-up Visit will be performed 28 days (+ 5-day window) after the End of Treatment/Early Withdrawal Visit.

Subjects who discontinue the IMP or withdraw from the trial early will attend the Safety Follow-up Visit according to procedures described in Sections 5.5.1 or 5.5.2, respectively.

Any ongoing SAEs must be followed up until the SAE/AE has resolved, is considered stable, or is considered no longer clinically relevant by the Investigator.

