**Table 22 : Data Handling for Safety Analysis**

Population	Period covered	Treatment groups	Data to be analyzed
SAF	12-week treatment period	
 
Placebo
 
Evobrutinib 25 mg QD
 
Evobrutinib 75 mg QD
 
Evobrutinib 50 mg BID
 
	All Data collected during the 12-week treatment period, safety follow-up included
Subjects with at least 1 dose during OLE	OLE period only	
 
Placebo/Evobrutinib 50 mg BID
 
Evobrutinib 25 mg QD/Evobrutinib 50 mg BID
 
Evobrutinib 75 mg QD/Evobrutinib 50 mg BID
 
Evobrutinib 50 mg BID/Evobrutinib 50 mg BID
 
	Data from OLE period only including all Safety follow-up data posterior to OLE (Safety follow-up / End of Study)

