**Table 43: Time Windows for Urinalysis**

Treatment groups	Period covered	Interval (days) [Date of assessment – Date of first dose + 1]	Analysis Visit

 
• Placebo
 
• Evobrutinib 25 mg QD
 
• Evobrutinib 75 mg QD
 
• Evobrutinib 50 mg BID
 
	12-week treatment period	1	Day 1
		[ 2 ; 70 )	Week 8 – Day 56
		[ 70 ; 91 )	Week 12 – Day 84

 
• Placebo/Evobrutinib 50 mg BID
 
• Evobrutinib 25 mg QD/Evobrutinib 50 mg BID
 
• Evobrutinib 75 mg QD/Evobrutinib 50 mg BID
 
• Evobrutinib 50 mg BID/Evobrutinib 50 mg BID
 
	OLE period	1	Day 1 – OLE
		[ 2 ; 45 )	Month 1 – OLE
		[ 45 ; 75 )	Month 2 – OLE
		[ 75 ; 105 )	Month 3 – OLE
		[ 105 ; 150 )	Month 4 – OLE
		[ 150 ; 225 )	Month 6 – OLE
		[ 225 ; 315 )	Month 9 – OLE
[ 315 ; 367 )	Month 12 – OLE		

**Table 44: Time Windows for Vital Signs, Serum IgA, IgG, IgM, Total B cell counts, Plasma/serum collection for CCI, Hematology and Biochemistry**

Treatment groups	Period covered	Interval (days) [Date of assessment – Date of first dose + 1]	Analysis Visit

 
• Placebo
 
• Evobrutinib 25 mg QD
 
• Evobrutinib 75 mg QD
 
• Evobrutinib 50 mg BID
 
	12-week treatment period	1	Day 1
		[ 2 ; 21 )	Week 2 – Day 14
		[ 21 ; 42 )	Week 4 – Day 28
		[ 42 ; 70 )	Week 8 – Day 56
		[ 70 ; 91 )	Week 12 – Day 84

 
• Placebo/Evobrutinib 50 mg BID
 
• Evobrutinib 25 mg QD/Evobrutinib 50 mg BID
 
• Evobrutinib 75 mg QD/Evobrutinib 50 mg BID
 
• Evobrutinib 50 mg BID/Evobrutinib 50 mg BID
 
	OLE period	1	Day 1 – OLE
		[ 2 ; 45 )	Month 1 – OLE
		[ 45 ; 75 )	Month 2 – OLE
		[ 75 ; 135 )	Month 3 – OLE
		[135 ; 225 )	Month 6 – OLE
		[ 225 ; 315 )	Month 9 – OLE
[ 315 ; 367 )	Month 12 – OLE		

*Note: Plasma/serum collection for CCI are not collected during OLE*

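### The visible safety time windows have no Safety Follow-up visit: completers' follow-up results get no analysis visit, and on one reading of the SAP early stoppers' off-drug results are summarised as Week 4, 8 or 12

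*SAP*

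**What the plan says.** SAP Section 9.6 (Time windows) re-allocates data so that "each measurement is allocated to the closest time point". It then states: "The analysis visit will then be used for all missing data imputations, analysis variable derivations, statistical calculations and presentations". The nominal visit is kept only for display in listings.

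The clock in Appendix 18.6 is "Interval (days) [Date of assessment – Date of first dose + 1" and nothing else; no visible row refers to last dose or to treatment status. Three readable tables matter here:

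- Table 44, "Time Windows for Vital Signs, Serum IgA, IgG, IgM, Total B cell counts" and also hematology and biochemistry: the last row of the 12-week period is Week 12, Days 70 to 90.
- Table 45 (B-cell subsets): the last row is Week 12, Days 56 to 90.
- Table 52 (HBV DNA): the last row is Week 12, Days 70 to 90.

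None has a follow-up row. Protocol Table 1 schedules all of these parameters at the Week 16 follow-up visit, and protocol Section 7.1.4 says: "The Safety Follow-up Visit will be performed 28 days (+ 5-day window) after the End of Treatment/Early Withdrawal Visit". Early stoppers attend too: "Subjects who discontinue early must return for the End of Treatment/Early Withdrawal Visit and Safety Follow-up Visit" (protocol Section 7.1.2).

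SAP Table 22 defines the 12-week safety data as "All Data collected during the 12-week treatment period, safety follow-up included". SAP Sections 15.3 and 15.4 say that laboratory values and vital signs will be presented at each scheduled time point.

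**The concern.** The SAP commits itself to analysing follow-up data but gives them no visible place in the visit structure that governs the analysis. Read literally, the windows can do one of two things with a follow-up record. They can leave it without a visit, so that it drops out of the by-visit tables. Or they can attach it to whichever on-treatment visit lies in its day range, because the rule looks only at days since first dose.

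Change from baseline in vital signs, immunoglobulins, total B cells and laboratory parameters are key secondary safety endpoints (protocol Section 8.3.2). If follow-up records drop out, the by-visit summaries and boxplots show nothing after treatment ends. If they are mislabelled, a summary headed Week 8 contains subjects who have been off drug for a month, and more of them in any arm with more early stopping. B-cell subsets (Table 45) share the gap but are not a key secondary safety endpoint.

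**Working it through.** **Inputs.** Week 12 is Day 84, with a visit window of -5 days and no plus side; Week 16 is Day 112 (protocol Table 1). "The End of Treatment Visit will be performed at Week 12 or within 5 days of early discontinuation of treatment with the IMP" (protocol Section 7.1.2.1). Follow-up is 28 to 33 days after that visit (Section 7.1.4). Window bounds come from SAP Tables 44, 45, 47, 51 and 52.

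**1. The plan's own figure.** 84 + 28 = 112, which agrees with protocol Table 1.

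**2. Completers.** Earliest follow-up: 84 - 5 + 28 = Day 107. Latest: 84 + 33 = Day 117. The last window ends at Day 90 in Tables 44, 45 and 52, so every day from 107 to 117 has no analysis visit.

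**3. Early stoppers.** With last dose on Day s, the End of Treatment visit is on s to s + 5 and follow-up on s + 28 to s + 38. If follow-up counts as part of the 12-week period:

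| Last dose (Day) | Follow-up (Days) | Visit under Tables 44 and 52 |
|---|---|---|
| 1-3 | 29-41 | Week 4 |
| 4-13 | 32-51 | Week 4 or 8 |
| 14-31 | 42-69 | Week 8 |
| 32-41 | 60-79 | Week 8 or 12 |
| 42-52 | 70-90 | Week 12 |
| 53-62 | 81-100 | Week 12 or none |
| 63-83 | 91-121 | none |

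Example: last dose on Day 20 gives follow-up on Days 48 to 58, which is Week 8 in Table 44. Under Table 45, last dose on Days 1-17 gives Week 4, Days 18-27 Week 4 or 12, and Days 28-52 Week 12; later stops are as above.

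A rule for choosing between duplicate records would not cure this in Table 44. Its widest window is Days 42 to 69, a spread of 27 days, and follow-up comes at least 28 days after the End of Treatment visit. The two records therefore never share a window.

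**4. Late Week 12 samples.** The inner bounds are midpoints: (14 + 28)/2 = 21, (28 + 56)/2 = 42, (56 + 84)/2 = 70. The next midpoint is (84 + 112)/2 = 98, which the efficacy and MRI windows use (Tables 47 and 51). The safety windows stop before Day 91. Day 91 is 7 days from Day 84 and 21 from Day 112; Day 97 is 13 and 15 days away. Days 91 to 97 are thus closest to Week 12 but unassigned.

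**5. Size of the mislabelling.** The documents give no distribution of stopping times. Assume 11% of 90, about 10 stops per arm, spread evenly over 84 days, with all attending follow-up. With follow-up 28 days after last dose, 13, 28 and 21 stopping days lead to Weeks 4, 8 and 12: 10 x 13/84 = 1.5, 10 x 28/84 = 3.3 and 10 x 21/84 = 2.5 records per arm. At 38 days the counts are 3, 28 and 21 days: 0.4, 3.3 and 2.5 records. That is 0.4% to 3.7% of a 90-subject arm at any one visit. The range for an arm in total is 0 (all stop from Day 63) to 10 (all stop by Day 52).

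**6. Size of the gap for completers.** On the same planning figure, about 80 subjects per arm, 4 x 80 = 320 in all, would have follow-up results without an analysis visit.

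**The case against.** Four points can be made on the other side.

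- **Redaction.** The opening text of Appendix 18.6 and Table 42 (supplementary liver tests) are not visible, and the title of Table 50 is blacked out. A general rule for follow-up records would naturally sit in that opening text. This stands: the finding describes the tables that can be read, and such a rule cannot be excluded.
- **Scope of the windows.** Each row is limited to the 12-week treatment period, and SAP Table 6 places follow-up after that period. On that reading no early stopper is mislabelled. This also stands as a reading, but Table 22 and the TEAE definition in Table 23 count follow-up within the period. And if Table 6 governs, no follow-up result from any subject has a visible analysis visit, so the gap becomes wider.
- **Little is lost.** Listings show nominal and analysis visit, TEAE tables do not use the windows, and these safety parameters carry no hypothesis test. This is right, and it limits the consequence. The worst-post-baseline shift tables are not by visit, but the SAP does not say whether a record without an analysis visit enters them.
- **Days 91 to 97.** A Week 12 sample in that range is at least 7 days late under a visit window with no plus side, so it should be rare. That is fair; the gap conflicts with the closest-time-point principle but is the smallest part of the point.

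**Conclusion.** The point holds as a gap and an ambiguity in the visible windowing rules. Completers' follow-up results have no analysis visit on either reading. Early stoppers' follow-up results are either labelled Week 4, 8 or 12 (always for a last dose on Days 1 to 52, sometimes for Days 53 to 62) or have no visit either. Both outcomes conflict with Table 22 or with the purpose of a by-visit summary. The mislabelling is probably a few records per arm per visit, given about 10 evenly spread stops per arm who all attend follow-up. The primary ACR20 analysis is untouched, because subjects who stop treatment are non-responders there.

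A reader might infer more: that on-treatment summaries are shown to be contaminated by about 40 off-drug records (11% of 360) and that the active arms are pulled toward baseline. The documents do not support this. Misallocation depends on one of two conflicting readings and on text that is redacted. The 11% covers noncompliance as well as dropout. The 40 would include about 10 placebo subjects, stops after Day 62, and subjects lost to follow-up or withdrawing consent, who may never attend. Nothing visible shows that these parameters return toward baseline within about 28 days of stopping.

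**What to change.** In SAP Appendix 18.6, unless the redacted opening already does so:

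1. Add a Safety Follow-up analysis visit to Tables 44, 45 and 52, assigned from the nominal visit before any day-based windowing.
2. Restrict the Week 2 to Week 12 windows to records up to and including the End of Treatment/Early Withdrawal visit, and before the first dose in the open-label extension.
3. Extend the Week 12 safety window to Day 98, as in the efficacy and MRI windows. Tables 43 and 46 (urinalysis and ECG) also end before Day 91, but neither is scheduled at follow-up, so only this item concerns them. Items 2 and 3 must go together: without the cut, a window to Day 98 would always capture follow-up for a last dose up to Day 60 (60 + 38 = 98) and could capture it up to Day 70 (70 + 28 = 98).
4. As a precaution, apply the same cut to hsCRP in Table 47, which is also drawn at follow-up. Table 12 already limits efficacy data to the Week 12 visit, so this only makes the rule explicit.
5. State in one sentence whether follow-up belongs to the 12-week period, so that Tables 6 and 22 agree, and whether follow-up values enter the worst-post-baseline shift tables.

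The cost is a few table rows, a sentence and one flag in the windowing program. No new data are needed, and it can be done before database lock.
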